14.9.5 Neuropsychiatric events

Neuropsychiatric events (in particular depression, anxiety and suicide ideation or behavior) will be tabulated separately based on the SMQ = 'Depression and suicide/self-injury'. The SMQ search should include all TEAEs which code to a PT included in the Scope=Broad and/or Scope=Narrow groups within the SMQ.

14.9.6 Inflammatory bowel disease

Inflammatory bowel disease events will be tabulated separately, based on the HLGT = 'Colitis excl infective'.

14.9.7 Anaphylactic reaction

Anaphylactic reactions will be summarized together in a stand alone table with the following incidence rows:

- The first row within the body of the table will be labeled 'Any hypersensitivity/anaphylactic reaction' and will represent the overall incidence of subjects who reported at least 1 hypersensitivity reaction or at least 1 anaphylactic reaction
- The second row within the body of the table will be labeled 'Any hypersensitivity reaction' and will represent the overall incidence of subjects who reported at least 1 hypersensitivity reaction
- The third row within the body of the table will be labeled 'Any anaphylactic reaction' and will represent the overall incidence of subjects who reported at least 1 anaphylactic reaction

Following these three overall incidence rows, all TEAEs that have been identified as either a hypersensitivity reaction or an anaphylactic reaction will be summarized by SOC, HLT and PT (these will not be presented by subcategory).

Hypersensitivity reactions and anaphylactic reactions will be identified as follows:

- **Hypersensitivity reactions:** all TEAEs with onset (start date/time) within 24 hours after any administration of IMP, which code to a PT which contains the term 'hypersensitivity' will be considered to be a hypersensitivity reaction and included in the summary table
- **Anaphylactic reactions:** An algorithmic approach will be used to identify TEAEs that are considered to be anaphylactic reactions. Preferred terms are separated into 4 distinct categories (A, B, C, D) prior to the algorithmic approach being applied.

All TEAEs with onset (start date/time) within 24 hours after any administration of IMP, and which fulfill any of the 3 criteria described in [Section 14.9.7.1](#) will be included in the summary table.

Any TEAEs with missing start time will be assumed to have occurred at the time of or after dosing for this purpose, if the event date is on the same day as a dosing date.

14.9.7.1 Anaphylactic reaction algorithm

The SMQ = 'anaphylactic reaction' consists of 3 parts:

- A **narrow search** containing PTs that represent core anaphylactic reaction terms. If a subject reports any TEAE which codes to a PT included in Category A, then the event will be flagged as an anaphylactic reaction and summarized as such in the table

– **Category A**

1. Anaphylactic reaction
2. Anaphylactic shock
3. Anaphylactic transfusion reaction
4. Anaphylactoid reaction
5. Anaphylactoid shock
6. Circulatory collapse
7. Dialysis membrane reaction
8. Kounis syndrome
9. Shock
10. Shock symptom
11. Type I hypersensitivity

A **broad search**: If a subject reports any TEAE which codes to a PT included in Category B **AND** reports any TEAE which codes to a PT included in Category C, **and both TEAEs have the same start date**, then both events will be flagged as anaphylactic reactions and summarized as such in the table

– **Category B**

1. Acute respiratory failure
2. Asthma
3. Bronchial oedema
4. Bronchospasm
5. Cardio respiratory distress
6. Chest discomfort
7. Choking
8. Choking sensation
9. Circumoral oedema
10. Cough
11. Cyanosis
12. Dyspnoea
13. Hyperventilation
14. Irregular breathing

-
15. Laryngeal dyspnoea
 16. Laryngeal oedema
 17. Laryngospasm
 18. Laryngotracheal oedema
 19. Mouth swelling
 20. Nasal obstruction
 21. Oedema mouth
 22. Oropharyngeal spasm
 23. Oropharyngeal swelling
 24. Respiratory arrest
 25. Respiratory distress
 26. Respiratory dyskinesia
 27. Respiratory failure
 28. Reversible airways obstruction
 29. Sensation of foreign body
 30. Sneezing
 31. Stridor
 32. Swollen tongue
 33. Tachypnoea
 34. Throat tightness
 35. Tongue oedema
 36. Tracheal obstruction
 37. Tracheal oedema
 38. Upper airway obstruction
 39. Wheezing

– **Category C**

1. Allergic oedema
2. Angioedema
3. Erythema
4. Eye oedema
5. Eye pruritis
6. Eye swelling

-
7. Eyelid oedema
 8. Face oedema
 9. Flushing
 10. Generalised erythema
 11. Injection site urticaria
 12. Lip oedema
 13. Lip swelling
 14. Nodular rash
 15. Ocular hyperaemia
 16. Oedema
 17. Periorbital oedema
 18. Pruritis
 19. Pruritis allergic
 20. Pruritis generalised
 21. Rash
 22. Rash erythematous
 23. Rash generalized
 24. Rash pruritic
 25. Skin swelling
 26. Swelling
 27. Swelling face
 28. Urticaria
 29. Urticaria papular

– **Category D**

1. Blood pressure decreased
2. Blood pressure diastolic decreased
3. Blood pressure systolic decreased
4. Cardiac arrest
5. Cardio respiratory arrest
6. Cardiovascular insufficiency
7. Diastolic hypertension
8. Hypotension

- An **algorithmic approach**: If a subject reports any TEAE which codes to a PT included in Category D **AND** reports (either a TEAE which codes to a PT included in Category B **OR** a TEAE which codes to a PT included in Category C), **and both TEAEs have the same start date**, then both events will be flagged as anaphylactic reactions and summarized as such in the table

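### The SAP's typed anaphylaxis term lists contain a raised-pressure term in the low-pressure group and four misspelt pruritus terms, so cases can be misclassified if those lists are used as written

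*SAP*

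**What the plan says.** SAP 14.9.7 reports anaphylactic reactions in a stand-alone table with its own overall incidence row. Events must start within 24 hours after a dose and meet one of three criteria in SAP 14.9.7.1:

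- any Category A term;
- a Category B term and a Category C term with the same start date;
- a Category D term and either a B or a C term with the same start date.

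Under the second and third criteria, both events are flagged. Section 14.9.7.1 names the MedDRA standardised query (SMQ) for anaphylactic reaction and then types out all four categories in full.

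Category D contains "Blood pressure decreased", "Blood pressure diastolic decreased", "Blood pressure systolic decreased" and *Hypotension*. It also has two arrest terms and one cardiovascular insufficiency term. Its seventh item is "Diastolic hypertension".

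Category C has 29 terms. Four use the spelling *pruritis*: *Eye pruritis*, *Pruritis*, "Pruritis allergic" and "Pruritis generalised". The list also prints "Rash generalized" beside "Generalised erythema".

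SAP 3.8 fixes MedDRA version 19.0 for coding adverse events. None of the changes in SAP Section 15 touches these lists.

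**The concern.** Category D is there to bring in cardiovascular collapse. A raised diastolic pressure is not that kind of event, and nothing in the SAP explains why it is listed. A programmer who follows the text would count it whenever a respiratory or skin term shares its start date.

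The spelling matters for a different reason. The rule asks whether an event's coded preferred term is in the category. A misspelt entry in a list matched as text will not meet the correctly spelt dictionary term, so the event drops out without any warning.

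The protocol names hypersensitivities among its adverse events for special monitoring (11.1.1.4), and safety is part of the secondary objective. In arms of about 40, 20 and 20 subjects, the anaphylaxis row can change visibly on a single subject.

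**Working it through.** There is no planned figure to reproduce. The check is a term count followed by an application of the printed rules.

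**Term counts.**

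- Category D has 8 terms: 4 low-pressure, 3 arrest or circulatory insufficiency, 1 raised-pressure. 4 + 3 + 1 = 8.
- Category C has 29 terms: 4 are misspelt and 1 is inconsistent in its -ized ending. *Eye pruritis* is an eye term, so three of the four misspellings are skin terms.

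**Rule applied.** A case is flagged if (B and C) or (D and (B or C)), with all events on the same start date and inside the 24-hour window. Categories C and D were entered as printed, with *Dyspnoea*, *Wheezing* and *Cough* standing in for Category B, and terms were matched exactly. The rule was then rerun with item 7 read as *Diastolic hypotension*, *pruritis* as *pruritus* and *generalized* as *generalised*. Those three readings are assumptions, because the SMQ list is not in the documents.

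| Same-day events | As printed | After correction |
|---|---|---|
| Diastolic hypertension alone | not flagged | not flagged |
| Diastolic hypertension + Cough | flagged | not flagged |
| Diastolic hypertension + Erythema | flagged | not flagged |
| Hypotension + Dyspnoea | flagged | flagged |
| Diastolic hypotension + Dyspnoea | not flagged | flagged |
| Diastolic hypotension + Urticaria | not flagged | flagged |
| Dyspnoea + Pruritus | not flagged | flagged |
| Hypotension + Pruritus generalised | not flagged | flagged |
| Dyspnoea + Rash generalised | not flagged | flagged |
| Dyspnoea + Urticaria + Pruritus | flagged | flagged |

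**What the table shows.**

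- Item 7 never flags a case alone. It needs a same-day B or C event.
- A misspelling loses a case only when the misspelt term is the sole qualifying Category C term. Even then, a case with both a B and a D term is still caught by the third criterion, and a case with a Category A term by the first.

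**The time window.** Protocol 11.3.3 has vital signs taken before dosing. SAP 14.9.7 treats an event on a dosing day with no start time as occurring at or after dosing. A raised pressure found before the injection and recorded as an adverse event without a time could therefore enter the window.

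**Scale of one case.** 1/40 = 2.5% of the bimekizumab arm and 1/20 = 5% of either comparator arm. This is the weight of any single subject, not an estimate of how often misclassification would happen.

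**The case against.** The best defence is that the SMQ, not the typed list, is the real specification. Section 14.9.7.1 opens by naming it, events are coded in MedDRA, and several neighbouring special-monitoring categories (for example SAP 14.9.3 to 14.9.5 and 14.9.8) are defined by SMQ search alone. A program that reads the dictionary's SMQ file would be exposed to neither problem. This stands as a condition on the spelling point. It does not dispose of item 7, because the criteria refer to the typed categories and the SAP nowhere says that the SMQ file overrides them.

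It is also fair that little is lost from reporting. Category A is untouched. All treatment-emergent events are tabulated by preferred term, and all adverse events are listed with onset times (SAP 11.2). The anaphylaxis table itself shows preferred terms, so a diastolic hypertension row would be visible. The SAP attaches no decision rule to that table. All of this stands and limits the consequence. The separate hypersensitivity row would not recover a missed case, since it takes only terms containing the word hypersensitivity.

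A reader might infer four stronger things that the documents do not support:

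- *Itching disappears from the algorithm.* It does not: *Rash pruritic* is spelt correctly and still matches, as do urticaria, rash, erythema and the other skin terms.
- *Any high diastolic pressure becomes anaphylaxis.* The event must be coded to that one term and have a same-day B or C companion. No other raised-pressure term is listed.
- *The generalised rash term fails to match.* Only an inconsistency within the list is shown; the dictionary spelling is not in the documents.
- *Low diastolic pressure is uncovered.* Two other Category D terms cover it at least in part, and the documents do not show how MedDRA 19.0 would code such an event.

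**Conclusion.** The point holds. Item 7 of Category D runs opposite to the other blood-pressure terms in its group, and following the SAP as written would count some raised-pressure events as anaphylactic reactions. That conclusion needs only the printed text.

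The spelling point is conditional: it produces missed cases only if the typed list is matched as text and the case does not qualify by another route. The count is four misspelt terms and one inconsistent term out of 29.

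That item 7 was meant to read *Diastolic hypotension* is an inference from the rest of Category D. *Pruritus* is the ordinary medical spelling. Both should be confirmed against the dictionary.

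The effect is limited to one descriptive special-monitoring safety table. The primary analysis is unaffected. The correction is worth making because the printed rule is wrong and the remedy is small.

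**What to change.** 1. Check Category D item 7 against the anaphylactic reaction SMQ in MedDRA 19.0 and correct it; the context suggests *Diastolic hypotension*.
2. Check the four *pruritis* entries and the generalised rash entry in Category C against the same source and correct them as needed.
3. State in SAP 14.9.7.1 that the SMQ term list for the coding version, matched on preferred-term code, governs, and that the typed lists are for reference.
4. Before the run, verify that every listed term resolves to a preferred term in that version.

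The cost is an appendix correction and one programming check.

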14.9.8 Hepatic events and drug induced liver injury

Hepatic events will include:

- Events based on the SMQ = ‘Drug related hepatic disorders – comprehensive search (excluding sub SMQs = ‘Liver neoplasms, benign [incl cysts and polyps]’ and ‘Liver neoplasms, malignant and unspecified’). All AEs should be included in the tabulation (included those considered both related and not related to the IMP) which code to a PT included in the Scope=Narrow group within each SMQ
- Hy’s Law cases will also be summarized separately in a table of liver function abnormalities as described in [Section 11.3](#) (with adjudication for PDILI cases)

14.10 Treatment group assignment for the TFLs

The treatment group labels and tabulation requirements for each data type are displayed in [Table 14–11](#).

Table 14–11: Treatment group assignment for the TFLs

TFL group	Placebo	Adalimumab	Bimekizumab	All Subjects
Subject disposition	X	X	X	X
Protocol deviations	X	X	X	X
Demographics	X	X	X	X
HS history and Baseline characteristics	X	X	X	X
Medical history	X	X	X	X
Prior/concomitant medications	X	X	X	X
AEs	X	X	X	
Safety data (including vital signs, ECG and laboratory tests)	X	X	X	
Pharmacodynamic data	X	X	X	
Efficacy data	X	X	X	
Pharmacokinetic data			X	
Anti-BKZ antibody			X	

AEs=adverse events; ECG=electrocardiogram.

15 AMENDMENTS TO THE SAP

15.1.1 Rationale for the amendment

Various updates were suggested prior to and during the interim analysis in late 2018.

15.1.2 List of changes

Change #1

List of Abbreviations

The following abbreviations have been added:

mHiSCR25	modified Hidradenitis Suppurativa Clinical Response – 25%
mHiSCR75	modified Hidradenitis Suppurativa Clinical Response – 75%
mHiSCR90	modified Hidradenitis Suppurativa Clinical Response – 90%
PDILI	potential drug-induced liver injury
PoC	proof of concept

Change #2

Introduction (Section 1), 2nd and 3rd paragraphs

This SAP is based on, and assumes familiarity, with the following documents:

- Protocol Amendment 1, dated 08 March 2018
- Primary Analysis Document, dated 19 September 2017

Unless specified in the sections below, the study will be analyzed as described in the most recent version of the protocol. If a future protocol amendment necessitates a substantial change to the statistical analysis of the study data, this IA SAP will be amended accordingly. In addition, if analysis definitions have to be modified or updated prior to the cut-off for IA, an IA SAP amendment will be required. However, if any additional analyses are required to supplement the planned analyses after the cut-off, these analyses will be described in a separate analysis plan.

Has been changed to:

This SAP is based on, and assumes familiarity, with the following documents:

- Final protocol amendment 1, dated 08 March 2018

Unless specified in the sections below, the study will be analyzed as described in the most recent version of the protocol. If a future protocol amendment necessitates a substantial change to the statistical analysis of the study data, this SAP will be amended accordingly. In addition, if analysis definitions must be modified or updated prior to database lock, a further SAP amendment will be required. If, after database lock, additional analyses are required to supplement the planned analyses described in this SAP, these changes will be described in the CSR together with the associated rationale.

Change #3

Determination of sample size (Section 2.4), 2nd paragraph

Additionally, the study has an exploratory objective to informally compare BKZ against the current standard of care for HS (ADA) using the 60% credible interval for the treatment difference.

Has been changed to:

Additionally, the study has an exploratory objective to informally compare bimekizumab against the current standard of care for HS (adalimumab) using the 60% credible interval for the treatment difference.

Change #4

Determination of sample size (Section 2.4), 5th paragraph

These simulations were based on Bayesian augmented control models in which the published summary data were used to construct informative priors for the PBO and ADA treatment arms in the current study. Based on historic data, the Bayesian model assumes an informative prior distribution for the PBO group HiSCR rate to be β (5.52,14.48). This prior distribution contributes an approximate effective sample size of 20 subjects for the PBO treatment group. Similarly, the Bayesian model assumes an informative prior distribution for the ADA group HiSCR rate to be β (11.78, 8.22), which, with the parametrization in the model, is equivalent to an ADA response rate of 58.9%. This prior distribution contributes an approximate effective sample size of 20 subjects for the ADA group. For the BKZ HiSCR rate, a vague prior probability distribution $N(0,1E4)$ was assumed.

Has been changed to:

These simulations were based on Bayesian augmented control models in which the published summary data were used to construct informative priors for the placebo and adalimumab treatment arms in the current study. Based on historic data, the Bayesian model assumes an informative prior distribution for the placebo group HiSCR rate to be β (5.52,14.48). This prior distribution contributes an approximate effective sample size of 20 subjects for the placebo treatment group. Similarly, the Bayesian model assumes an informative prior distribution for the adalimumab group HiSCR rate to be β (11.78, 8.22) which, with the parametrization in the model, is equivalent to an adalimumab response rate of 58.9%. This prior distribution contributes an approximate effective sample size of 20 subjects for the adalimumab group. For the bimekizumab HiSCR rate, a vague prior probability distribution $N(0,1E4)$ was assumed.

Change #5

Protocol Deviations (Section 3.4), 3rd paragraph

At least 3 data evaluation meetings (DEMs) will be performed for this study at the following time points:

- Prior to the formal unblinded interim analysis planned after approximately 45 subjects have completed 4 weeks of the study.
- Prior to the informal unblinded interim analysis planned after the last subject has completed 12 weeks of the study or has discontinued early.
- Prior to the final analysis after all subjects have completed the SFU period and data have been verified/coded/entered into the database

Has been changed to:

At least 3 data evaluation meetings (DEMs) will be performed for this study at the following time points:

- Prior to the informal unblinded interim analysis planned after approximately 45 subjects have completed 4 weeks of the study.
- Prior to the informal unblinded interim analysis planned after the last subject (excluding 2 subjects from site 101 in Australia who entered the study outside of the original planned recruitment period) has completed 12 weeks of the study or has discontinued early.
- Prior to the final analysis after all subjects have completed the SFU period and data have been verified/coded/entered into the database

Change #6

Changes to protocol-defined analyses (Section 3.9)

This final bullet has been added:-

- Based on the second interim analysis for this study, additional exploratory efficacy variables based on the lesion count assessment data, HiSCR depth and disease flare status, have been defined in this SAP amendment. [Section 8.2.4](#) includes details on the derivation of different HiSCR depths and [Section 8.2.5](#) describes the planned summaries of this additional variable. [Section 8.3.1.2](#) defines disease flare and includes details on planned summaries of disease flare status and the number of visits at which a subject experienced a disease flare during the Treatment Period.

Change #7

Dates (Section 4.2.4)

This final paragraph has been added:-

Partially missing dates will be imputed as described above and the duration of each AE will be calculated in days as follows:

$$\text{Duration of AE} = (\text{Date of Outcome} - \text{Date of Onset}) + 1$$

Change #8

Calculation rules for duration of adverse events (Table 4-1)

This table has been removed.

Change #9

Interim analysis (Section 4.5.2)

A formal unblinded non-binding interim analysis will be conducted when approximately 45 subjects have completed 4 weeks of the study. During this interim analysis, the sample size assumptions will be checked and the final sample size may be modified if the sample size assumptions at study planning are no longer accurate. Also, at this interim analysis, the study may be stopped for futility. Sample size re-estimation criteria and methods along with futility

rules and operating characteristics will be detailed in the Interim Analysis SAP. The futility rule will be chosen such that the overall power of the study remains high.

An informal, unblinded interim analysis will be performed when the last randomized subject for this study has completed the Week 12 Visit at the end of the Treatment Period or this subject's participation has ended prematurely. The purpose of this informal interim analysis is for the Sponsor key personnel to review the results of the primary efficacy analysis and safety outcomes to facilitate additional Clinical Planning or Portfolio Management decisions. Details on the summaries and analyses to be presented at this informal interim analysis will be included in the Interim Analysis SAP.

All analyses and unblinding instructions will be pre-specified in the Interim Analysis SAP.

Has been changed to:

This study will include two informal unblinded interim analyses, the first after approximately 45 subjects have completed 4 weeks of the study and the second when the last randomized subject for this study has completed the Week 12 Visit at the end of the Treatment Period or this subject's participation has ended prematurely. This second planned interim analysis excludes the 2 subjects from site 101 who entered the study outside of the recruitment period. The purpose of these interim analyses is for sponsor key personnel to review results from the primary efficacy analysis and a subset of the analyses of exploratory efficacy and safety outcomes to facilitate additional Clinical Planning or Portfolio Management decisions. Neither interim analysis will lead to any formal decision to alter or terminate the trial.

Details on the summaries and analyses to be presented at these informal interim analyses are included in the Interim Analysis SAP.

All analyses and unblinding instructions will be pre-specified in the Interim Analysis SAP.

Change #10

Hidradenitis suppurativa history (Section 6.5)

Detailed information of each subject's HS history will be collected at Screening and will include, but will not be limited to, the following:

- Date of Initial Diagnosis of HS
- Date HS Symptoms First Started
- The date, onset, and duration of past treatments for HS
- The date of any prior surgeries for HS

The HS history will be listed based on the RS.

Has been changed to:

Date of initial diagnosis of HS and the date that HS symptoms first started will be listed.

Change #11

Prior and concomitant medications (Section 6.6), 3rd and 4th paragraphs

Separate summaries will be presented for the following, identified using WHODD Anatomical Main Group codes, the indication recorded on the eCRF and medical review of the recorded data:

- Prior and concomitant HS medications
- Concomitant antibiotic medications at study entry
- Rescue therapy medication during study

All HS medications will be confirmed at the DEMs prior to unblinding.

Has been changed to:

Separate summaries will be presented for the following, identified using WHODD Anatomical Main Group codes, the indication recorded on the eCRF and medical review of the recorded data:

- Prior and concomitant HS medications
- Concomitant antibiotic medications at study entry
- Rescue medication during study

All HS medications, antibiotics and rescue medication given during the study will be identified via medical review of the concomitant medications and confirmed at the DEMs prior to unblinding.

Concomitant antibiotic medication at study entry is defined as any antibiotic that was ongoing or started on the Screening visit.

Change #12

Bayesian Modelling (Section 8.2.2.1), 9th paragraph

To protect against severe forms of study to study variation and/or miss-matches between Baseline Hurley Stage subject proportions and effect sizes, a prior data conflict test will be conducted using the above priors as detailed in [Section 8.2.2.3](#) and vague priors for the PBO and ADA treatment groups will be used if either of the two null hypotheses of no prior data conflict are rejected at the 95% confidence level. The prior data conflict test also provides some protection against model miss-specification – for example if there turns out to be a Baseline Hurley Stage by treatment group interaction as the PIONEER II data suggest.

Has been changed to:

To protect against severe forms of study to study variation and/or mismatches between Baseline Hurley Stage subject proportions and effect sizes, prior data conflict will be investigated for all informative priors through use of graphical displays. If there is evidence of prior data conflict for a given parameter, then a vague prior will be used for that parameter. Investigating any prior data conflict also provides some protection against model misspecification – for example if there turns out to be a Baseline Hurley Stage by treatment group interaction as the PIONEER II data suggest.

Change #13

Building the Prior (S8.2.2.2), final paragraph

If further information (independent to this study) regarding the PBO group response comes to light then the priors for this analysis may be updated prior to study unblinding, and details of this will be supplied in an amendment to this SAP or the CSR. In this case the priors will still be based upon historic data only.

Has been changed to:

If further information (independent to this study) regarding the PBO and/or ADA treatment group response rates comes to light then the priors for this analysis may be updated prior to study unblinding, and details of this will be supplied in an amendment to this SAP or the CSR. In this case the priors will still be based upon historic data only.

Note that the informative priors for the PBO and ADA treatment group response rates may be updated based upon any observed differences in the proportions of Baseline Hurley Stage II and III subjects as long as no response rate data from the current study, blinded or unblinded, are taken into consideration. For example, if updated, these priors may be fitted by Baseline Hurley Stage if the relative proportions of Baseline Hurley Stage II and III subjects within the current study differ substantially from those reported in the historical data. In this case the priors will still be based only on historic response data, but using the Hurley-stage specific information rather than the average information.

Change #14

Prior data conflict (Section 8.2.2.3)

For each of the PBO and ADA groups separately, the prior data conflict test will consist of comparing the observed minimal sufficient statistic for the Binomial distribution (the number of HS events) to the prior predictive distribution of this minimal sufficient statistic.

Has been changed to:

Prior data conflict will be investigated for all informative priors through use of graphical displays. If there is evidence of prior data conflict for a given parameter, then a vague prior will be used for that parameter.

Change #15

Supportive and sensitivity analyses of the primary efficacy variable (Section 8.2.3), 1st paragraph

The primary efficacy analysis set is the PPS, however the primary analysis and all supportive and sensitivity analyses of the primary efficacy variable will be repeated using the FAS.

Additionally, the comparison of the BKZ treatment group to the ADA treatment group is reported under the following sections.

Has been changed to:

The primary efficacy analysis set is the PPS, however the primary analysis and all supportive and sensitivity analyses of the primary efficacy variable will be repeated using the FAS.

The comparison of the BKZ treatment group to the ADA treatment group is described specifically in this section as a sensitivity analysis, however, it must be noted that the results

from the BKZ versus ADA comparison will be presented for completeness in each of the sensitivity analyses described in [Section 8.2.3.1](#) to [8.2.3.10](#) below.

Change #16

Comparison of bimekizumab and adalimumab (Section 8.2.3.2)

In addition to the primary comparison of the BKZ and PBO treatment groups, the comparison between BKZ and ADA in HiSCR at Week 12 will be performed using the methods as described above in [Section 8.2.2.4](#) for the primary efficacy analysis. This will be an informal comparison to assess whether any improvements in response rate observed with BKZ (over PBO) are comparable to the current standard of care (ADA).

Has been changed to:

In addition to the primary comparison of the BKZ and PBO treatment groups, the comparison between BKZ and ADA in HiSCR at Week 12 will be performed using the methods as described above in [Section 8.2.2.4](#) for the primary efficacy analysis. A 60% credible interval will be presented for the BKZ versus ADA comparison. This will be an informal comparison to assess whether any improvements in response rate observed with BKZ (over PBO) are comparable to the current standard of care (ADA); it will not be part of the evaluation of PoC for this study.

Change #17

Frequentist analysis – NRI (Section 8.2.3.7), 1st paragraph

An estimate of the treatment difference (BKZ versus PBO) at Week 12 will be obtained from a longitudinal generalized estimating equation (GEE) model for a binary outcome, controlling for Baseline Hurley Stage and including treatment, visit and a treatment by visit (week) interaction term. An unstructured covariance matrix will be used for this analysis. In the event that the model does not converge, alternate covariance structures will be considered.

Has been changed to:

An estimate of the treatment differences (BKZ versus PBO and BKZ versus ADA) at Week 12 will be obtained from a longitudinal generalized estimating equation (GEE) model for a binary outcome, controlling for Baseline Hurley Stage and including treatment, visit and a treatment by visit (week) interaction term. An unstructured covariance matrix will be used for this analysis. In the event that the model does not converge, alternate covariance structures will be considered.

Change #18

Concomitant antibiotic use – Frequentist analysis (Section 8.2.3.9), 1st paragraph

An estimate of the treatment difference (BKZ versus PBO) at Week 12 will be obtained from a longitudinal GEE model for a binary outcome, controlling for Baseline Hurley Stage and including concomitant antibiotic use at study entry (coded as a binary [yes/no] variable), treatment, visit, treatment by visit (week) interaction term and antibiotic use by Baseline Hurley Stage interaction terms. Missing response data will not be handled using NRI (ie, observed cases analysis).

Has been changed to:

An estimate of the treatment differences (BKZ versus PBO and BKZ versus ADA) at Week 12 will be obtained from a longitudinal GEE model for a binary outcome, controlling for Baseline

Hurley Stage and including concomitant antibiotic use at study entry (coded as a binary [yes/no] variable), treatment, visit, treatment by visit (week) interaction term and antibiotic use by Baseline Hurley Stage interaction terms. Missing response data will not be handled using NRI (ie, observed cases analysis).

Change #19

HiSCR depth (Section 8.2.4)

This section has been added:

As an additional exploratory analysis of HiSCR, the algorithm applied to derive response at each visit (as described in [Section 8.2.1](#)) will be adapted to evaluate varying depths of HiSCR during the Treatment Period. A modified HiSCR will be calculated using different criteria for % Δ AN, namely 25%, 75% and 90%, in order to derive a response at each visit. In the summaries of HiSCR depth, the primary efficacy variable will be referred to as HiSCR and the other depth variables referred to as modified (m)HiSCR25, mHiSCR75 and mHiSCR90.

Change #20

Presentation of HiSCR (Section 8.2.5)

The HiSCR will be listed together with the component efficacy data as specified in [Section 8.3.1](#).

The number and percentage of subjects who achieved HiSCR will be tabulated by treatment group and visit, based on the PPS. A summary will also be presented by Baseline Hurley Stage. All summaries will include the 95% CI for the percentage of subjects with an HiSCR, calculated using a Wilson approximation. The summary will be presented based on NRI and repeated for observed cases. For the observed cases analysis, the denominator for the percentage calculations will be the number of subjects with non-missing HiSCR data in the PPS for each treatment group, visit and Baseline Hurley Stage (as applicable).

All tabulations described in this section will be repeated for the FAS. For the observed cases analysis, the denominator for the percentage calculations will be the number of subjects in the FAS for each treatment group, visit and Baseline Hurley Stage (as applicable) with non-missing HiSCR data. Listings will be presented for the SS.

A figure will be presented showing the percentage of subjects who achieved HiSCR, together with 95% CIs, over time. All treatment groups will be overlaid on the same plot. The plot will be generated based on the PPS and the FAS.

Additionally, the following bar charts will be presented showing the percentage of subjects who achieved HiSCR at Week 12:

- by treatment group and Baseline Hurley Stage
- by treatment group, Baseline Hurley Stage and antibiotic use at study entry
- by treatment group, Baseline Hurley Stage and rescue therapy use at any time during the study

Has been changed to:

HiSCR will be listed together with the component efficacy data as specified in [Section 8.3.1](#). This listing will include the different HiSCR depth variables (i.e. mHiSCR25, HiSCR, mHiSCR75 and mHiSCR90).

The number and percentage of subjects who achieved HiSCR will be tabulated overall by treatment group and visit, and also by Baseline Hurley Stage and by concomitant antibiotic use at study entry; and also by Baseline Hurley Stage and rescue medication use at any time during the study. This summary will be presented for the PPS and will include the 95% CI for the percentage of subjects with an HiSCR, calculated using a Wilson approximation. The summary will be presented based on NRI and repeated for observed cases. For the observed cases analysis, the denominator for the percentage calculations will be the number of subjects with non-missing HiSCR data in the PPS for each treatment group, visit and Baseline Hurley Stage or concomitant antibiotic use at study entry (as applicable).

The number and percentage of subjects who achieved mHiSCR25, mHiSCR75 and mHiSCR90, together with 95% confidence intervals, will be presented overall and by Baseline Hurley Stage, and by treatment group and visit based on observed cases for the PPS.

All tabulations described in this section will be repeated for the FAS. For the observed cases analysis, the denominator for the percentage calculations will be the number of subjects in the FAS for each treatment group, visit and Baseline Hurley Stage or concomitant antibiotic use at study entry (as applicable) with non-missing HiSCR data. Listings will be presented for the SS.

A figure will be presented showing the percentage of subjects who achieved HiSCR, together with 95% CIs (calculated using a Wilson approximation), over time. All treatment groups will be overlaid on the same plot. The plot will be generated based on NRI and observed cases for the PPS and the FAS. These plots will be repeated for the percentage of subjects who achieved the different HiSCR depths; mHiSCR25, mHiSCR75 and mHiSCR90.

Additionally, for the PPS and FAS, based on NRI and observed cases, the following bar charts will be presented showing the percentage of subjects who achieved HiSCR during the Treatment Period:

- by treatment group and visit
- by treatment group, visit and Baseline Hurley Stage
- by treatment group and Baseline Hurley Stage at Week 12
- by treatment group, Baseline Hurley Stage and concomitant antibiotic use at study entry, at Week 12
- by treatment group, Baseline Hurley Stage and rescue medication use at any time during the study, at Week 12

